#### 7.2.5 Adverse Event Relationship

The investigator must assess each AE's relationship to the IP. The investigator must carefully consider possible when assigning a relationship of specific AEs to study drug. The categories for classifying the investigator's opinion of the relationship are as follows:

#### Not Related

This is an AE that is clearly not related to the study drug beyond a reasonable doubt. That is, another cause of the event is more plausible; and/or a clinically plausible temporal sequence is inconsistent with the onset of the event and the administration of study drug and/or a causal relationship is considered biologically implausible.

## **Unlikely Related**

This is an AE that could reasonably be considered caused by something else, and where there is no known or expected response pattern to the suspect study drug.

#### **Possibly Related**

This category applies to an AE that follows a reasonable temporal sequence from administration of the study drug and that follows a known or expected response pattern to the suspected study drug, but that could readily have been produced by a number of other factors.

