# 7.2.6 Expectedness

An expected adverse drug reaction has a nature or severity that is consistent with the study intervention description as found in the Investigator Brochure (for unapproved investigational products). An adverse drug reaction is unexpected if it is not listed in the Investigator Brochure or is not listed at the specificity or severity that has been observed. Determination of expectedness is the responsibility of the sponsor and is necessary for determining if the event is a suspected unexpected serious adverse reaction which is reported to FDA and IRB in an expedited manner. The purpose of expedited reporting is to make regulators, investigators, and other appropriate personnel aware of new, important information on serious reactions. Such reporting will generally involve events previously unobserved or undocumented.

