### 10.3. Adverse Events

An adverse event (AE) is defined as any untoward medical occurrence in a patient or clinical investigation patient administered an IP that does not necessarily have a causal relationship with this treatment. An AE can therefore be any unfavorable and unintended sign (including an abnormal laboratory finding, for example), symptom, or disease temporally associated with the use of a medicinal product, whether related to the medicinal product, or not.

Pre-existing diseases or conditions will not be considered AEs unless there is an increase in the frequency or severity, or a change in the quality, of the disease or condition. Worsening of a pre-existing condition is considered an AE.

Events that occur in patients treated with placebo, or during treatment free periods of the study, are also considered AEs.

An AE is defined as treatment-emergent if the first onset or worsening is during or after the first administration of IP and not more than 30 days after the last administration of study drug. In the case of missing or partial dates, an adverse event will be considered treatment-emergent unless the available data excludes that possibility.

An AE summary table will present totals for the following:

- All treatment-emergent adverse events (TEAEs)
- TEAEs by severity
- TEAEs leading to study drug discontinuation
- TEAEs by relationship (not related, unlikely related, possibly related)
- SAEs
- AEs of Special Interest (AESIs [See below])

Summaries of incidence rates (frequencies and percentages) of individual AEs by MedDRA SOC and preferred term will be prepared. Such summaries will be displayed for all TEAEs, TEAEs by maximum severity, and TEAEs by strongest relationship to study drug.

Each patient will be counted only once within each summation level (SOC; preferred term). If a patient experiences more than one TEAE within each summation level, the TEAE with the strongest relationship or the maximum severity, as appropriate, will be included in the summaries of relationship and severity.

All AEs will be presented in a listing.

These summaries will include SAEs; additionally, they will be presented separately (see below).

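### The causality scale in protocol 7.2.5 has no literal place in its top level for a well-timed adverse event that lacks a known pattern or lacks an alternative cause, which distorts the TEAE-by-relationship rows only

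*Protocol*

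**What the plan says.** Protocol 7.2.5 requires a causality assessment for each AE and introduces a closed list: "The categories for classifying the investigator's opinion of the relationship are as follows". Three levels follow.

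- **Not Related:** "This is an AE that is clearly not related to the study drug beyond a reasonable doubt". The text explains this as another cause being more plausible, and/or inconsistent timing, and/or biological implausibility.
- **Unlikely Related:** two joined conditions, given as "could reasonably be considered caused by something else, and where there is no known or expected response pattern to the suspect study drug". Both must hold.
- **Possibly Related:** the timing element reads "This category applies to an AE that follows a reasonable temporal sequence from administration of the study drug". The pattern and alternative-cause elements, which must hold as well, read "follows a known or expected response pattern to the suspected study drug, but that could readily have been produced by a number of other factors".

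SAP 10.3 carries the same list into the AE summary table: "TEAEs by relationship (not related, unlikely related, possibly related". The match shows that no higher level was lost when the protocol was converted from PDF. Protocol 10.7.3 plans TEAE incidence by relationship, and SAP 10.3 adds tables by system organ class and preferred term showing the strongest relationship.

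Two other provisions matter. Protocol 7.2.6 treats expectedness as a separate determination by the sponsor. Protocol 7.2.2 puts a Yes/No question on the SAE form, asking whether there is a reasonable possibility that the product caused the event; that question does not mention a known pattern.

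**The concern.** A causality scale should rise with the strength of the case for the drug: good timing, biological plausibility and no better explanation. This one departs from that in two ways.

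First, the top level requires that the reaction already be recognised in some sense. An unrecognised reaction therefore cannot reach it, however good the timing. That brings expectedness into the investigator's causality judgement, although 7.2.6 gives expectedness to the sponsor.

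Second, the top level also requires a ready alternative explanation. An event that nothing else could explain, which is the strongest causal case, does not meet the definition.

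Safety and tolerability compared with placebo is one of the two objectives in protocol section 2, and section 1 describes the trial as proof of concept, so unrecognised reactions are of interest. At stake is whether the planned relationship rows mean what a reader of the study report will take them to mean.

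**Working it through.** The plan gives no figure on this point, so there is nothing to reproduce. The check applies the three definitions literally to every combination of three attributes:

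- timing: plausible or not;
- known or expected pattern: yes or no;
- alternative cause: none, other factors could explain the event, or another cause is more plausible.

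Reading rules: the elements of Unlikely Related and of Possibly Related are joined and must all hold. A more plausible other cause also counts as an available alternative. Causation is taken not to be biologically implausible, since otherwise Not Related applies in any case.

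Results when timing is plausible:

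| Known pattern | Alternative cause | Level that fits |
|---|---|---|
| No | None | No level |
| No | Other factors could explain | Unlikely Related |
| No | Other cause more plausible | Not Related and Unlikely Related |
| Yes | None | No level |
| Yes | Other factors could explain | Possibly Related |
| Yes | Other cause more plausible | Not Related and Possibly Related |

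When timing is not plausible, Not Related is available in all six combinations, so the difficulty lies in the well-timed cases. Among those:

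- No row without a known pattern reaches Possibly Related (0 of 3).
- Both rows without an alternative cause fit no level (2 of 2), and a known pattern does not help.
- Two of the six rows fit two levels at once.

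An event that fits no level has no rule to place it. SAP 10.3 deals with missing dates but not with a missing relationship, and SAP 10.1 excludes imputation for safety data.

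Which outputs use the scale:

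- **Affected:** TEAEs by relationship (protocol 10.7.3, SAP 10.3) and by strongest relationship (SAP 10.3).
- **Not affected:** all TEAEs, TEAEs by severity, SAEs, AESIs and TEAEs leading to discontinuation (SAP 10.3 and 10.4).

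The documents give neither a rate of drug-caused events nor the share without a known pattern, so the size cannot be derived. The following illustrates the mechanism only, on assumed inputs. Take n = 100 in one active arm (300 planned, 1:1:1), true incidence p of drug-caused events, and share f without a known pattern. Assume that every drug-caused event with a known pattern is recorded as Possibly Related. The expected number of patients in that row is then n × p × (1 − f).

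| p (assumed) | f = 0 | f = 0.25 | f = 0.50 |
|---|---|---|---|
| 5% | 5 | 3.8 | 2.5 |
| 10% | 10 | 7.5 | 5 |
| 20% | 20 | 15 | 10 |

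**The case against.** The strongest reply is that investigators do not apply such definitions as logic. Faced with a symptom after every dose and no other explanation, an investigator has one upward choice, Possibly Related, and will probably use it. That may well happen, and it is one reason the size is unknown. But the relationship rows would then rest on an unwritten convention that can differ between sites, so the wording is still worth correcting.

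A second reply is that the randomised comparison of safety comes from AE incidence by arm, with attribution only supplementary. This stands. An excess of a new event on active treatment would still appear in the all-TEAE tables, and no formal safety test uses the scale. Nasal irritation, the most obvious local reaction, is also an AESI, and SAP 10.4 tabulates its timing relative to dosing.

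Three stronger readings are tempting, but the documents do not support them.

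- **Every AE missing from the Investigator's Brochure is barred from Possibly Related.** Protocol 7.2.5 does not mention the Brochure. The Brochure test, "An adverse drug reaction is unexpected if it is not listed in the Investigator Brochure", belongs to 7.2.6. An unlisted event may still follow a pattern that an investigator would expect; 7.2.8.1 itself describes theoretical antidiuretic, electrolyte, blood-pressure and ECG effects. Only events outside any known or expected pattern are affected in this way.
- **A drug-related AE table is biased low.** The SAP defines no pooled drug-related table. It shows each level, so events filed as Unlikely Related remain visible by arm.
- **Expedited reporting of unexpected reactions breaks down.** The suspected unexpected reactions in 7.2.6 are serious events, and the SAE form asks its own question without a pattern condition. The protection is partial, because 7.2.5 still applies to SAEs and the two answers could disagree, but no failure of reporting is shown.

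**Conclusion.** The definitions in protocol 7.2.5 are defective as written. A non-serious AE with plausible timing but no known pattern is placed in Unlikely Related when another cause is conceivable. A well-timed AE with no alternative cause fits no level, with or without a known pattern. The effect is limited to the relationship and strongest-relationship rows, and its size cannot be derived from the documents.

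The direction, too few events in the top row, rests on literal use of the definitions. If investigators treat Possibly Related as a catch-all, the undercount shrinks or disappears, but the rows still cannot separate a clear drug effect from a possible coincidence. The conclusion also assumes that the conditions within each definition are cumulative, which is how the sentences are built.

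**What to change.** In protocol 7.2.5:

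1. Delete the pattern condition from both Unlikely Related and Possibly Related, and leave expectedness to the sponsor under 7.2.6.
2. Word the top level so that it covers events with plausible timing whether or not another cause could explain them. State that such an event belongs there rather than in Unlikely Related, because without the pattern clause both definitions could otherwise fit. State also when a more plausible other cause moves it to Not Related.

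Alternatively, replace the three levels with the SAE form's existing Yes/No question, applied to all AEs. That also removes the possibility of two conflicting answers for one serious event.

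Update the relationship rows in SAP 10.3 to match, and add a line on how an AE with a missing relationship is tabulated.

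The cost is wording in the protocol, CRF and SAP, plus table rows. The count in the top relationship row may rise. The protocol is already at Amendment 4, so AEs may already have been entered; those may need a one-time re-query, best done while the study is still blinded. Deleting the pattern clause and widening the top level is the smaller change; replacing the scale is optional.

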# 7.2.6 Expectedness

An expected adverse drug reaction has a nature or severity that is consistent with the study intervention description as found in the Investigator Brochure (for unapproved investigational products). An adverse drug reaction is unexpected if it is not listed in the Investigator Brochure or is not listed at the specificity or severity that has been observed. Determination of expectedness is the responsibility of the sponsor and is necessary for determining if the event is a suspected unexpected serious adverse reaction which is reported to FDA and IRB in an expedited manner. The purpose of expedited reporting is to make regulators, investigators, and other appropriate personnel aware of new, important information on serious reactions. Such reporting will generally involve events previously unobserved or undocumented.

# 7.2.7 Clinical Significance

An abnormal laboratory value or test result, e.g., ECG, is clinically significant if the abnormality suggests a disease and/or there is organ toxicity that is new or worsened from Baseline.

#### 7.2.8 Special Considerations

# 7.2.8.1 Adverse Events of Special Interest

Since IN administrations of agents can cause significant irritation of nasal mucosa, events of nasal irritation will be followed closely during the study and considered an AE of Special Interest. Investigators should monitor for tissue changes or lesions in the visualized nasal mucosa on nasal exam, and for pain or discomfort anywhere in the nasal cavity, sinuses or oropharynx.

Because intranasal administration of oxytocin can result in a transient, albeit short-lived and minor, rise in systemic oxytocin levels, there will be specific monitoring for the potential adverse effects of supraphysiological levels of oxytocin in plasma. It should, however, be noted that with intranasal administration and the proposed oxytocin dosing regimens, sustained and clinically relevant plasma oxytocin levels are not expected. It is out of an abundance of caution that close monitoring for potential safety signals will be carried out.

Theoretically, if substantial and sustained concentrations in plasma are achieved, plasma oxytocin may activate off target vasopressin receptors leading to antidiuretic effects. Thus, AEs that may involve changes in blood volume, blood pressure, and specific electrolyte disturbances (hyponatremia) will be AEs of special interest, e.g., new onset edema, hypervolemia, increased blood pressure, ECG changes related to cardiac hypertrophy or arrhythmia.

## 7.2.8.2 Pregnancy

All women of childbearing potential who participate in the study should be counseled on the need to practice adequate birth control and on the importance of avoiding pregnancy during study participation. Women should be instructed to contact the investigator or study staff immediately if pregnancy occurs or is suspected.

Pregnancy testing will be conducted prior to administration of the IP on every woman of childbearing potential. A woman who is found to be pregnant at the Screening Visit will be excluded from the study and considered to be a SF.

A woman who becomes pregnant during IP treatment or within 28 days of discontinuing the IP will be immediately discontinued from study participation. The investigator must report the pregnancy as if it were an SAE within 48 hours of learning of the pregnancy, to using the Pregnancy Data Collection Form via the same fax number and/or email address as for SAE reporting. The investigator should contact the designated individual(s) who receive SAE notification and record information related to the pregnancy on a designated form provided by the sponsor or its designee.

Early Termination Visit assessments are required as soon as possible after learning of the pregnancy. The investigator is also responsible for following the pregnancy until delivery or termination. These findings must be reported on the designated form and forwarded to the designated individual(s). The event meets the SAE criterion only if it results in a spontaneous abortion after the first trimester or a congenital anomaly.

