Oxytocin is a nonapeptide produced in the supraoptic and paraventricular nucleus of the hypothalamus which is released into the systemic circulation through the posterior pituitary gland (Moller, 2021). There are also collateral oxytocin producing neurons from the hypothalamus that project to diverse brain regions such as nucleus accumbens and amygdala. Oxytocin's physiological functions include regulation of uterine contractility in pregnant women and milk ejection in lactating women. In the central nervous system (CNS), oxytocin is a mediator of pro-social behavior and fear response. Oxytocin is approved by the Food and Drug Administration (FDA) for intravenous use to induce labor in pregnant women as well as for the treatment of postpartum hemorrhage. Intranasal oxytocin is used in Europe for inducing labor in pregnant women and for enhancing milk production in lactating women.

Oxytocin exerts analgesic effects when administered intrathecally in the rodent model. This effect appears to be receptor specific since it was blocked by an oxytocin antagonist (Tzabazis, et al., 2017). The therapeutic index of intrathecal oxytocin is large, i.e., 270-fold when considering analgesic versus severe side effects and 400-fold when considering analgesic effects versus lethality. Oxytocin is thought to mediate its analgesic action in part via the endogenous opioid system. Diverse CNS sites may be involved in mediating such

analgesic effects, since oxytocinergic neurons display widespread projections throughout the CNS.

Nonclinical studies have confirmed that oxytocin accumulates in the ganglion of the trigeminal nerve after intranasal administration in rats (Tzabazis, et al., 2017). These rats showed site-specific analgesic effects when stimulated in the face (innervated by the trigeminal nerve) but not when stimulated at the hind paw.

A single study in humans suggested that intrathecal injection of oxytocin may prove useful as an analgesic treatment modality. Oxytocin reduced back pain in dose-dependent fashion and a dose of 0.5 IU/kg of oxytocin provided complete relief in about 83% of patients studied (Yang, 1994).

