## 7.1.3.2 Serious Adverse Events

#### 7.1.4 Serious Adverse Events

A serious adverse event (SAE) is defined by federal regulation as any AE occurring at any dose that results in any of the following outcomes: death, life-threatening AE, hospitalization or prolongation of existing hospitalization, a persistent or significant disability/incapacity, or a congenital anomaly/birth defect.

Important medical events that may not result in death, be life-threatening, or require hospitalization may be considered an SAE when, based upon appropriate medical judgment, they may jeopardize the patient and may require medical or surgical intervention to prevent one of the outcomes listed in this definition. Examples of such medical events include allergic bronchospasm requiring intensive treatment in an emergency room or at home, blood dyscrasias or convulsions that do not result in patient hospitalization, or the development of drug dependency or drug abuse.

Any SAE that occurs at any time during the study, including a clinically significant abnormal laboratory test result that is considered serious, must be reported to Tonix or its designee(s) so that Tonix may comply with regulatory obligations. If the SAE is life-threatening or fatal, it must be reported to Tonix or its designee(s) immediately, by facsimile and telephone. For these and all other SAEs, an SAE Report Form must be completed and sent by facsimile or email to Tonix or its designee(s) within 1 working day of the site's initial awareness of the event. These requirements apply equally to all patients, regardless of the study period or the at-risk patient's treatment assignment or dosage.

A SAE (experience) or reaction is any untoward medical occurrence that, at any dose:

Results in death,

- Is life-threatening,
- Requires in-patient hospitalization or prolongation of existing hospitalization,
- Results in persistent or significant disability/incapacity,
- Is a congenital anomaly/birth defect, or
- Is an important medical event.

NOTE: The term "life-threatening" in the definition of "serious" refers to an event in which the patient was at risk of death at the time of the event. It does not refer to an event that hypothetically might have caused death if it were more severe.

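### The exclusive SAE rule for pregnancy in Protocol 7.2.8.2 contradicts the general SAE definition in 7.1.4, so some serious pregnancy events could go unclassified as SAEs

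*Protocol*

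**What the plan says.** Protocol 7.1.4 defines an SAE by outcome: "death, life-threatening AE, hospitalization or prolongation of existing hospitalization, a persistent or significant disability/incapacity, or a congenital anomaly/birth defect". It then widens the definition by medical judgment: "Important medical events that may not result in death, be life-threatening, or require hospitalization may be considered an SAE" when the patient may be put in jeopardy or need intervention. A bulleted restatement in the same section includes "Requires in-patient hospitalization or prolongation of existing hospitalization". On reporting, it adds: "These requirements apply equally to all patients, regardless of the study period". Nothing in 7.1.4 mentions pregnancy or trimester, apart from congenital anomaly as one of the qualifying outcomes.

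Protocol 7.2.8.2 sets a separate procedure for pregnancies. On notification: "The investigator must report the pregnancy as if it were an SAE within 48 hours of learning of the pregnancy", using a dedicated form. On follow-up: "The investigator is also responsible for following the pregnancy until delivery or termination". It closes with its own seriousness rule: "The event meets the SAE criterion only if it results in a spontaneous abortion after the first trimester or a congenital anomaly."

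SAP 10.4 tabulates SAEs by system organ class and preferred term. SAP 10.3 tabulates treatment-emergent AEs and lists all AEs. SAP 10.5 puts pregnancy test results in listings. The SAP has no rule for classifying pregnancy events and plans no table of pregnancy outcomes.

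**The concern.** The closing sentence of 7.2.8.2 is exclusive. It gives two qualifying outcomes and, through *only if*, shuts out the rest of the 7.1.4 list. A site handling a pregnancy will naturally turn to the pregnancy section and may apply its closed list instead of the general definition.

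Classification has consequences. The SAE label decides whether an event enters the SAE summary. It also decides whether the sponsor's expectedness review in Protocol 7.2.6, which serves to identify unexpected serious reactions for expedited reporting, applies to the event. The reporting clocks differ too: 24 hours for an SAE (Protocol 7.2.2) and 48 hours for a pregnancy (7.2.8.2). The synopsis says that no formal safety data monitoring is planned, so the classification of single cases carries more weight than it otherwise would.

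Pregnancy outcomes deserve care in this trial. Women of childbearing potential are enrolled, and the Introduction lists among oxytocin's physiological functions "regulation of uterine contractility in pregnant women and milk ejection in lactating women". It also notes that the intranasal form is used in Europe to induce labor.

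**Working it through.** The plan gives no figure to reproduce. The check is a comparison of the two rules, event by event.

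| Pregnancy event | Under 7.1.4 | Under 7.2.8.2, read literally | Agreement |
|---|---|---|---|
| Congenital anomaly, whenever exposure occurred | SAE | SAE | Yes |
| First-trimester loss or complication with hospitalization | SAE | Not an SAE | **Conflict** |
| First-trimester complication that is life-threatening | SAE | Not an SAE | **Conflict** |
| First-trimester loss judged an important medical event | SAE by judgment | Not an SAE | **Conflict** |
| First-trimester loss meeting no 7.1.4 criterion | Not an SAE | Not an SAE | Yes |
| Later complication with hospitalization, but no loss or anomaly | SAE | Not an SAE | **Conflict** |

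The conflict therefore covers the events that meet a 7.1.4 criterion and fall outside the two-item list. It does not cover every early loss, and it is not confined to the first trimester.

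**Does any text settle precedence?** None does. Two features favor the general definition. Section 7.1.4 presents its definition as coming from federal regulation. The neighboring overdose section (7.2.8.3) treats an overdose as an AE or SAE according to whether the criteria are met, so it defers to 7.1.4. The pregnancy section substitutes its own list.

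**What follows if 7.2.8.2 is applied literally?** A conflict event loses its entry in the SAE summary (SAP 10.4) and the serious-reaction step of Protocol 7.2.6. If it is recorded as a treatment-emergent AE, it still appears in the tables of SAP 10.3, and it is listed in any case. The sponsor still receives the pregnancy notification and its outcome.

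**Can the size be derived from the visit schedule?** Only the timing of exposure can, and only with outside assumptions.

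- From the Schedule of Assessments: Visits 3, 4 and 5 are at Days 29, 57 and 85, each ±4 days, with a pregnancy test at every visit. The nominal gap is 57 − 29 = 28 days. The longest is 61 − 25 = 36 days (equally, 89 − 53 = 36).
- Assumed, not in the documents: a pregnancy can be missed for 7 to 14 days after conception, and gestational age is conception age plus 14 days.
- Gestation at detection, latest case = gap + missed days + 14. Lowest: 28 + 7 + 14 = 49 days (7.0 weeks). Highest: 36 + 14 + 14 = 64 days (9.1 weeks).

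If visits are kept, exposure on treatment would thus fall mostly or wholly in the first trimester. The rule turns on the type and timing of the *outcome*, however, so this range does not give the number of misclassified events.

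**The case against.** The strongest reply is that the word *event* in the disputed sentence may mean the pregnancy as recorded on its form. The sentence would then say only when the pregnancy outcome itself counts as serious, and a separate maternal complication would remain an ordinary AE judged under 7.1.4. That section is broad: it covers SAEs at any time during the study and separately requires any death to be reported at once. This reading is possible, and it means that omission from the SAE table is a risk and not a certainty. It does not remove the conflict, because an early loss with hospitalization is itself a pregnancy outcome and the two sections still disagree on it.

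The second reply is that little information is lost. Every pregnancy goes to the sponsor within 48 hours and is followed to its end, and anomalies count as serious. This stands: what is at stake is the SAE label and what depends on it.

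Several stronger inferences are tempting, and the documents do not support them:

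- *First-trimester harms are removed from the SAE tables.* This needs 7.2.8.2 to override 7.1.4, which no text says. An uncomplicated early loss is an SAE under 7.1.4 only by medical judgment, and an anomaly after early exposure still counts.
- *Nearly every exposed pregnancy is affected.* The timing calculation dates exposure. A normal delivery or an anomaly is not misclassified, and early exposure followed by a loss after the first trimester is on the 7.2.8.2 list.
- *The SAE comparison between arms is biased low.* The rule applies equally to all blinded arms, and no formal safety statistics are planned (Protocol 10.7.3, SAP 10.1). A count may be too low, but a biased contrast is not shown.
- *Early loss is an expected harm of this drug.* The Introduction describes uterine activity, but Protocol 7.2.8.1 does not anticipate lasting, clinically relevant plasma levels by this route. The step to early loss would need an outside source.

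**Conclusion.** The point holds as a contradiction between two operative sections: for a pregnancy event that meets a 7.1.4 criterion outside the two-item list, 7.1.4 says SAE and 7.2.8.2 says not. The sentence is wrong as written, not merely lacking in detail.

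The severity is low to moderate. The effect is a possible undercount of SAEs, and a possible gap in expedited-reporting assessment, if sites apply 7.2.8.2 literally. The documents give no rate for such events. Few are likely, because contraception is required at entry (subject to the stated exceptions) and pregnancy is tested at every visit. The efficacy analyses and the notification of pregnancies are untouched. A reader might see the safety-reporting context as making this critical to the trial, but the likely number of events and the separate pregnancy follow-up do not support that rating.

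The conclusion rests on the literal sense of *only if* and on the absence of a precedence rule. It does not depend on the timing assumptions.

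**What to change.** Reconcile 7.2.8.2 with 7.1.4. One way is to replace the exclusive sentence with a cross-reference stating that pregnancy outcomes and complications are classified by the criteria in Section 7.1.4. The pregnancy form, its notification deadline and follow-up to outcome would stay as separate requirements. Any SAE completion guidance that repeats the sentence should be aligned with the reconciled text.

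The cost is one sentence in a protocol amendment and possibly a few more SAE reports. SAP 10.4 needs no change, since it tabulates whatever is classified as an SAE.
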